6.2.4 Additional analyses

The following subgroups are defined for additional analyses (e.g. primary endpoint):

- Age > vs. <= 75 years old
- Gender male vs female
- Left ventricular ejection fraction >40% vs. <= 40% (EF)
- Diabetes yes vs no
- Prior bleeding yes vs no
- Prior cerebrovascular event yes vs no
- Device (Watchman 2.5 vs. Amulet), Watchman FLX vs Amulet
- Pre-procedural therapy with all combinations (none vs. SAPT vs DAPT vs. OAC vs. OAC+APT)

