6.2 Randomization

Balanced (1:1) randomization will be performed via a web-based interactive randomization system (ICE-Advice Pharma), based on a computer-generated random sequence with a random block size stratified according to site and allocation to either Amulet Amplatzer device or Watchman/FLX. In the event that the patient is randomized to the Watchman/FLX arm, the operator will be able to choose, on the basis of clinical reasons, if to implant Watchman or the new generation Watchman FLX (if available in the center). Randomization will occur as close as possible to but always before the procedure and once the patient is judged eligible and the informed consent has been signed.

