9.1.2 Randomization and Procedure

Patients who have signed the informed consent form and meeting all inclusion and exclusion criteria will be included in the study and randomized before LAAC procedure.

After randomization, patients will receive the LAAC with the randomized device. In the event that the patient is randomized to the Watchman/FLX group, the operator will be able to choose, on the basis of clinical reasons, if to implant Watchman or the new generation Watchman FLX (if available in the center).

In case of impossibility to implant the randomized device, the operator can change the device or stop the procedure

and the patient will be considered for crossover adjudication (see section 8.4).
Fluoroscopy images will be digitalized and encoded for adjudication.

The following evaluations will be performed before, during and after the procedure:

- 12 lead ECG
- TEE or ICE to guide intervention according to the current standard of care
- Procedure-related data collection including duration, fluoroscopic time and overall contrast medium dose as well as any procedure-related complications (described in 5.3)
- Collection of any Serious Adverse Event (SAE) and adverse events of special interest ([AESI] as defined in 11.1 and Appendix 1) up to 48 hours or discharge whichever comes first.

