2.2 Randomization

Balanced (1:1) randomization will be performed via a web-based interactive randomization system (ICE-Advice Pharma), based on a computer-generated random sequence with a random block size stratified according to site and an allocation to either Amulet Amplatzer device or Watchman/FLX. In the event that the patient is randomized to the Watchman/FLX arm, the operator will be able to choose, on the basis of clinical reasons, if to implant Watchman or the new generation Watchman FLX (if available in the center). Randomization will occur as close as possible to but always before the procedure and once the patient is judged eligible and the informed consent has been signed.

CTU Bern	Swiss APERO SAP	Version: 2.0	
	Template: CS_STA_TEM-11	Valid from: 17.08.2021	

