4.2 Analysis populations

The primary endpoint analysis will be performed using the intention to treat principle on the intention-to-treat, full-analysis set population. Sensitivity analyses will be performed on the per-protocol population. Crossover patients will be considered as a primary end-point event in all analyses.

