4.2.1 Full analysis set (FAS)

The full analysis set (FAS) will include all randomized subjects. Following the intent-to-treat principle, subjects will be analyzed according to the treatment they are assigned to at randomization.

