4.2.2 Per-protocol (PP)

Per-protocol population PP consists of all subjects in the FAS who do not have any major protocol violation. The following items will be considered such a major protocol deviations, which will exclude the patient from the PP (Table 2):

CTU Bern	Swiss APERO SAP	Version: 2.0	
	Template: CS_STA_TEM-11	Valid from: 17.08.2021	

Table 2: Derivation of major protocol violations used for PP definition.

Protocol deviation	eCRF sheet	Variable	Variable type	Derivation of violation
Violation of inclusion or exclusion criteria				
Age ≥ 18 years (ic1)	Baseline	age	Continuous	age<18
Written informed consent (ic2)	Baseline	ic2	Binary: yes/no	no
CHADS2VASC score ≥ 2 (ic5)	Baseline	{score based on baseline variables, add points into score}	Add points	hf=yes (1 point), hypertension=yes (1 point), age ≥ 75 (2 points) OR age 65-74 years (1 point), diabetes=yes (1 point), prior_cerebr=yes OR arterial_embolism=yes OR conc_th=yes (2 points), vasculopathy=yes OR prior_mi=yes OR aortic_plaque=yes (1 point), gender=female (1 point). Violation if score<2
HASBLED ≥ 3 or High bleeding risk HBR as defined by Munich consensus document (ic6)	Baseline	{score based on baseline variables, add points into score}	Add points	HASBLED: uncontroll=yes (1 point), kidney_disease=yes (1 point), liverdisease=yes (1 point), type_cerebr=stroke (1 point), priorbleeding=yes OR anemia=yes OR ind_primary={any of: history of major or minor bleeding, wish to avoid triple therapy, risk of fall, concomitant disease improving bleeding risk ,HASBLED ≥ 3 } (1 point) OR hb ≤ 130 g/L in male/hb <120 g/L in female, inab_oac_variability=3 (1 point), age >65 (1 point), bl_drugs_{oac, noac, aspirin, thienopyridine,fans }=any yes (1 point), alcohol=yes (1 point) HBR: priorbleeding=yes OR anemia=yes OR hb ≤ 130 g/L in male/hb <120 g/L in female Violation if score≤ 2 AND HBR=no
Exclusion criteria not met	Randomization	exclusion_criteria_exclusion_crit	Binary: yes/no	no
First LAAC device used not according to randomization	Procedure	first_device, first_imp_att	Categorical, Number	Equal to randomized but implantation attempts = 0 OR
	Procedure	first_device	Categorical	Unequal to randomized

CHADS2VASC: see <https://www.mdcalc.com/cha2ds2-vasc-score-atrial-fibrillation-stroke-risk>

HASBLED: see <https://www.mdcalc.com/has-bled-score-major-bleeding-risk>

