6.1 Outcome definitions

Outcomes will be compared randomized to Amulet vs randomized to Watchman.

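### SAP 6.2.4 sets each Watchman generation against Amulet, although the operator chooses the generation after allocation and the Amulet comparator is not defined

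*Combined protocol and SAP*

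**What the plan says.** Randomisation is 1:1 between Amulet and Watchman/FLX as one arm, stratified by site only (protocol 6.2, SAP 2.2). Within the Watchman/FLX arm, SAP 2.2 states that "the operator will be able to choose, on the basis of clinical reasons, if to implant Watchman or the new generation Watchman FLX". Protocol 6.2 adds the condition of availability: "if to implant Watchman or the new generation Watchman FLX (if available in the center"). On timing, protocol 9.1.2 says "After randomization, patients will receive the LAAC with the randomized device" and then describes the choice of generation.

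SAP 6.2.4 lists eight subgroup items. Seven are age, sex, ejection fraction, diabetes, prior bleeding, prior cerebrovascular event and pre-procedural therapy. The eighth is "Device (Watchman 2.5 vs. Amulet), Watchman FLX vs Amulet".

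The surrounding rules are:
- SAP 6.1: "Outcomes will be compared randomized to Amulet vs randomized to Watchman".
- SAP 4.2.1, for the full analysis set: "subjects will be analyzed according to the treatment they are assigned to at randomization".
- SAP 4.2: "Crossover patients will be considered as a primary end-point event in all analyses".
- SAP 5.5, Table 2: the procedural table separates Watchman from Watchman FLX only in its block for the final device.

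The protocol synopsis gives a planned start of February 2018 and says that FLX received its CE mark at the beginning of 2019.

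**The concern.** A subgroup fixed before allocation splits both arms in the same way, so each split is still a randomised comparison. Watchman generation splits one arm only, by a decision made after allocation. No Amulet patient has a corresponding value, because the documents do not ask for the intended generation to be recorded before randomisation.

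There are two routes to a misleading result:
- **Selection.** The protocol describes FLX as designed to fit a wider range of patients and to improve sealing, so a choice made on clinical grounds could follow anatomy. The primary outcome is patency or crossover, and crossover is adjudicated on sealing and stability (protocol 8.4). The choice may therefore track outcome risk.
- **Site and period.** Without a restriction, the FLX contrast can include Amulet patients randomised at a site, or at a time, without FLX.

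The generation-specific results could then differ from each other with no difference between the generations. The SAP lists them with ordinary baseline subgroups and gives no caveat.

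**Working it through.** **1. The plan's own figure.** SAP 2.3 claims more than 80% power for the whole-arm comparison with 50% vs 30% and 200 patients. Take 100 per arm and a two-sided 5% test (sidedness is not stated for this test, so this is an assumption):
- null SE = sqrt(2 × 0.4 × 0.6 / 100) = 0.0693, and × 1.96 = 0.1358
- alternative SE = sqrt((0.25 + 0.21) / 100) = 0.0678
- power = Φ((0.20 − 0.1358) / 0.0678) = Φ(0.947) = 82.8%

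The claim reproduces. It concerns the randomised arms and is not in question here.

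**2. What randomisation supports, by FLX availability at the site on the randomisation date.**
- *FLX not available:* the operator has no choice of generation. Watchman 2.5 vs Amulet patients at that site in that period is a randomised comparison. The documents do not show whether any such patients exist, since they give only a planned start and no enrolment or availability dates.
- *FLX available:* the operator chooses. The randomised comparison is Amulet vs Watchman/FLX as a mixture. Neither generation alone is randomised against Amulet.

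SAP 6.2.4 does not separate these two situations.

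**3. How selection acts (illustration; every input is assumed).** Suppose there is no true difference between any devices. Half the patients have difficult anatomy, with event risk r0 (easy) and r1 (difficult). FLX is chosen with probability s0 (easy) and s1 (difficult). Then FLX risk = (s0·r0 + s1·r1) / (s0 + s1), and Amulet risk = (r0 + r1) / 2 = 50%. With 50 FLX, 50 Watchman 2.5 and 100 Amulet patients:

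| r0 / r1 | s0 / s1 | FLX − Amulet | Watchman 2.5 − Amulet | Rejection at 5%, each contrast |
|---|---|---|---|---|
| 30% / 70% | 50% / 50% | 0 | 0 | 5% |
| 40% / 60% | 30% / 70% | +4 points | −4 points | about 7% |
| 30% / 70% | 30% / 70% | +8 points | −8 points | 15% |
| 30% / 70% | 20% / 80% | +12 points | −12 points | 28% |

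For the third row, FLX risk = (0.3 × 0.3 + 0.7 × 0.7) / 1.0 = 58%. The signs reverse if FLX goes to easier anatomy. The table shows the mechanism; it does not estimate the bias in this trial.

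**4. Precision after restriction.** Let F be the number of FLX patients and A the number per arm randomised with FLX available. Both are assumed, with F ≤ A and equal numbers per arm. The 95% CI half-width for FLX vs Amulet is 1.96 × sqrt(0.25/F + 0.21/A).
- F = 50: A = 100 gives 1.96 × sqrt(0.0071) = 16.5 points; A = 75 gives 1.96 × sqrt(0.0078) = 17.3; A = 50 gives 1.96 × sqrt(0.0092) = 18.8.
- F = 30: 20.0 (A = 100) to 24.3 (A = 30).
- F = 70: 14.8 (A = 100) to 15.9 (A = 70).

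**5. Precision of the availability subgroup.** In the level without FLX, 25 vs 25 patients give 1.96 × sqrt(0.46/25) = 26.6 points, and 50 vs 50 give 18.8. For the difference between levels, A = 75 gives sqrt(15.3² + 26.6²) = 30.7 and A = 50 gives sqrt(18.8² + 18.8²) = 26.6. If FLX was available throughout, there is no second level and no interaction to estimate.

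**The case against.** The strongest reply is that this is one line among eight in a section headed as additional analyses, and that the plan is open about it. Operator choice is disclosed in several sections, the item is labelled as a device comparison, and SAP 5.5 will report the counts of each device by arm. Analyses by device received are an accepted part of the plan: protocol 12.4 and SAP 4.1 provide for as-treated analyses, and SAP 4.2.3 and 5.9 go by the device implanted. On this view only a caveat is missing. Much of this stands, and it lowers the priority. It does not settle the matter, because an undefined comparator is more than a missing caveat, and restricting it removes the site and period mismatch.

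Four stronger readings are tempting, and the documents do not support them:
- *The contrasts breach the full-analysis-set rule.* SAP 4.2 ties that rule to the primary endpoint analysis, and the plan expressly allows as-treated analyses.
- *Restriction would make both contrasts randomised.* For FLX, the documents describe no patients for whom FLX vs Amulet would be randomised. Restriction leaves operator selection in place.
- *An availability subgroup is free of confounding.* Each level is a randomised comparison, but the levels differ from each other in site, period and possibly operator experience.
- *The restricted half-width has a ceiling of 18.8 points.* That figure holds for 50% vs 30% with 50 per group. At 50% vs 50% it is 1.96 × sqrt(0.5/50) = 19.6, and fewer Amulet comparators would widen it further.

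**Conclusion.** The concern holds in limited form. Both generation contrasts depend on a choice made after allocation in one arm, and the Amulet comparator is undefined. They can therefore reflect operator selection, site and period as well as the devices. The design may also contain a randomised Watchman 2.5 vs Amulet comparison, among patients randomised when FLX was not available at their site, and the SAP does not isolate it.

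The amount of bias is unknown. It depends on the FLX share, the availability periods and how operators chose, none of which the documents give; it could be zero if the choice was unrelated to risk. A reader might infer that the trial's main result is compromised. It is not: the primary comparison is by randomised arm, with both generations pooled as the design intends. Priority is minor to moderate, because only additional analyses are affected.

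**What to change.** 1. Add a subgroup by FLX availability at the site on the randomisation date (yes/no) and compare the arms as randomised within each level. If the level without FLX contains patients, report it as the randomised Watchman 2.5 vs Amulet comparison. Treat any difference between levels as exploratory, and say that the levels also differ in site, period and possibly operator experience.
2. If FLX vs Amulet is kept, limit the Amulet comparator to patients randomised at the same site while FLX was available. Label it exploratory and non-randomised, together with any Watchman 2.5 contrast that includes patients for whom FLX was available.
3. Classify generation by the first device attempted. By final device, a Watchman-arm patient crossed over to Amulet belongs to neither generation and drops out, although SAP 4.2 counts that patient as an event. SAP 4.2.2 already uses the first device for the exclusion "First LAAC device used not according to randomization", but its Table 2 shows the first_device field only as categorical. Confirm that the field separates the generations. List separately the Watchman-arm patients who cannot be classified, for example those with no implantation attempt.

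**Cost.** SAP wording, a check of one eCRF field, and FLX availability periods from each site, which may need more than one date if supply was interrupted. In the example with 50 FLX patients, the half-width for FLX vs Amulet rises from 16.5 points (100 comparators) to 18.8 (50 comparators). Power for an interaction is low, and the level with FLX can mix generations, so it answers a related question and not the pure device question.

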6.2.5 Assessment of statistical assumptions

Time-to-event curves will be compared and checked for the proportional hazards assumption using Schoenfeld's residuals.

6.3 Interim analyses

No statistical interim analyses are planned.

6.4 Missing data

The primary and secondary outcomes will be analyses in multiple imputed data-sets using chained equations and combining estimates and p-values using Rubin's rule, if requested.

6.5 Safety evaluation

The safety outcomes, AE and SAEs will be summarized in tables at all study periods, namely:

- Enrolment
- Procedure
- Post procedural hospital discharge
- 7 days
- 45-day follow-up
- 6-month follow-up
- 13-month follow-up
- 2-year follow-up
- 3-year follow-up
- 4-year follow-up
- 5-year follow-up

CTU Bern	Swiss APERO SAP	Version: 2.0	
	Template: CS_STA_TEM-11	Valid from: 17.08.2021	

6.6 Statistical software

Stata version 16.1 or higher and R version 4.03 or higher will be used.

6.7 Quality control

The primary and secondary outcomes will be double-programmed.

CTU Bern	Swiss APERO SAP	Version: 2.0	
	Template: CS_STA_TEM-11	Valid from: 17.08.2021	

7. References

CTU Bern	Swiss APERO SAP	Version: 2.0	
	Template: CS_STA_TEM-11	Valid from: 17.08.2021
